7.5.3 Subgroup Analyses

Subgroup analyses of ACR 20/50/70 responses, and DAS28-CRP/DAS28-ESR change from baseline will be provided by point estimates and 95% CI by treatment group at Week 12. The subgroup analyses will be performed using Efficacy analysis population. Subgroup factors and breakdown are listed in Table 2.

Table 2: Subgroup Analyses Factors and Categories

Subgroup Factor	Categories
Age	< 65 Years Old ≥ 65 Years Old
Gender	Male Female
Race	White Black Asian Other
Geographic Region Grouping Scheme A ^a	Latin America+Eastern Europe North America+Western Europe+ROW
Geographic Region Grouping Scheme B ^b	North America Latin America Europe ROW
Prior treatment	MTX-IR TNF-IR
# of TNFi failure	=1 =2

Table 2: Subgroup Analyses Factors and Categories

Subgroup Factor	Categories
Duration of Rheumatoid Arthritis	≤ 10 Years
	> 10 Years
Baseline DAS28-CRP	Baseline DAS28-CRP > 5.1
	Baseline DAS28-CRP ≤ 5.1

^a See region/country listin in [Appendix 3](#).

7.5.4 Sensitivity Analyses

If more than 10% of total subjects in the efficacy analysis population discontinued due to any reasons other than Lack of Efficacy (LOE), AE or Unknown reason, a sensitivity analysis may be performed. The subjects who have missing response due to premature discontinuation with reasons other than LOE, AE or Unknown will be excluded from the analyses, hence defining the sensitivity analysis population. The sensitivity analysis will be carried out for the primary and selected secondary endpoints (ACR20/50/70 response, DAS28-CRP and DAS28-ESR change from baseline) based on the sensitivity analysis population.

7.5.5 Per-Protocol Analyses

If at least 10% of total subjects in efficacy analysis population demonstrate relevant protocol deviations, a per-protocol analysis may be performed. A Per-protocol (PP) analysis population will exclude all subjects with at least one relevant protocol deviation (defined in [Appendix 1](#)) from the efficacy analysis population. A per-protocol analysis will be carried out for the primary and selected secondary endpoints (as defined in section 7.5.4) based on the PP analysis population. The grouping scheme will be the same as in the primary efficacy analysis.

7.6 Safety

Analysis of all safety data will follow the BMS standard safety data conventions^{[11](#) [12](#)} and supplements to the standard conventions as defined in this document.

The evaluation of drug safety is based primarily on clinical AE, laboratory abnormalities and vital signs reported during the study.

The summaries of AEs and laboratory marked abnormality during DB period will be provided by treatment groups. AEs and laboratory marked abnormalities will be included in the analysis of the DB period if the onset date is on or after first dose date and event occurs within 30 days post last dose date (DB period).

Frequency distribution and individual listings of all AEs will be generated. Laboratory marked abnormality using pre-defined abnormality criteria will also be descriptively summarized. There will be no statistical testing of group difference with respect to frequencies of AEs or laboratory marked abnormalities.

All recorded adverse events will be listed and tabulated by system organ class, preferred term, treatment and overall. Any physical examination findings will be listed. ECG, vital signs and clinical laboratory test results and corresponding change from baseline values will be listed and summarized by treatment. Values for ECG, vital signs and clinical laboratory test results outside the pre-specified criteria will also be listed and summarized. ECG readings will be evaluated by the Investigator and abnormalities, if present, will be listed.

Unless otherwise specified, baseline is defined as the last non-missing result with a collection date-time less than the date-time of the first dose of study medication, for laboratory results, vital signs and ECG.

Presentations for the DB period will be provided by “as treated” treatment group for as-treated analysis population, unless otherwise specified.

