4.5.1 Double Blind Period

All drug dosing should occur after all study-related assessments, including blood draws, are completed.

After randomization, study drug will be dispensed according to the assignment by the IVRS system. Doses of BMS-986142 at 100 mg, 200 mg, 350 mg or matching placebo are to be administered orally q24h (one time/day) with water and may be taken with or without food. Four tablets, one from each bottle, will be taken, all at the same time, once/day every day. **On Day 1, and at Week 2, 4, 8, and 12 study drug will be administered in the morning at the study site and after blood samples have been collected.** However, at other visits, drug should be taken at approximately the same time each day.

Study drug is blinded and is supplied in bottles. Each subject will be dispensed a set of four (4) bottles at each study visit. Each bottle contains 35 tablets of blinded study drug. The 5 additional tablets in each bottle allow for the ± 5 day window between each visit in the double-blind phase of the study. Study drug bottles that were dispensed to the subject must be brought back to the study site by the subject at Weeks 2, 4, 8, and 12 during the double-blind period.

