Subjects who discontinue at any time during the Treatment Period must complete the Early Termination (ET) Visit assessments							
Procedure	Day 1	Wk 2 (approx. D 15)	Wk 4 (approx. D 28)	Wk 8 (approx. D 56)	Wk 12 or ET (approx. D 84)	30 day FU Visit (approx. Day 114)	Notes
Safety Assessments							
Physical Exam	X				X	X	
Height and Weight	X				X	X	
ECG	X		X		X	X	Not required if early termination (ET) visit
Vital Signs	X	X	X	X	X	X	See Section 5.3.1 for details
Adverse Events Assessment	X	X	X	X	X	X	
Laboratory Assessments							
Hematology (CBC with differential)	X	X	X	X	X	X	
Chemistry panel	X	X	X	X	X	X	Must include liver function testing; see Section 5.3.5 for details. For double-blinded period, fasting glucose is required.
Estimated Glomerular Filtration Rate (eGFR) - AUDIT	X	X	X	X	X	X	As performed by Modification of Diet in Renal Disease (MDRD) Study equation
Fasting lipid panel	X			X	X	X	At least 10 hour fasting prior to collection of sample
IgM, IgA, and IgG	X		X		X	X	
Urinalysis	X				X	X	
Rheumatoid Factor	X				X	X	
Anti-CCP2	X		X		X	X	

Table 5.1-2: Flow Chart for Protocol IM006016 - Double-Blinded Treatment Period^a							
Subjects who discontinue at any time during the Treatment Period must complete the Early Termination (ET) Visit assessments							
Procedure	Day 1	Wk 2 (approx. D 15)	Wk 4 (approx. D 28)	Wk 8 (approx. D 56)	Wk 12 or ET (approx. D 84)	30 day FU Visit (approx. Day 114)	Notes
ANA	X				X	X	
Anti- Ro (SS-A) and Anti-La (SS-B)	X				X	X	
Urine pregnancy test	X		X	X	X	X	WOCBP only; results confirmed prior to administration of study drug. See Section 3.3.3
ESR (performed locally)	X	X	X	X	X	X	Performed locally. Every effort should be made to ensure the person analyzing the ESR results is not involved in the efficacy assessments (see Section 5.4)
hsCRP	X	X	X	X	X	X	
Pharmacokinetics	X	X	X	X	X		See Section 5.5.1 for details
Efficacy Assessments							
Tender (68)/ Swollen (66) Joint Count	X	X	X	X	X	X	Must have at least 6 swollen/tender joints prior to randomization
Subject Assessment of Pain	X	X	X	X	X	X	QoL assessments; see Section 5.8
Subject's Global Assessment of Disease Activity	X	X	X	X	X	X	
Physician's Global Assessment of Disease Activity	X	X	X	X	X	X	
Physical Function (HAQ-DI)	X	X	X	X	X	X	
Fatigue (VAS)	X				X	X	
SF-36	X				X	X	

Table 5.1-2: Flow Chart for Protocol IM006016 - Double-Blinded Treatment Period^a							

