6 STUDY PERIODS, TREATMENT REGIMENS AND POPULATIONS FOR ANALYSES

6.1 Study Periods

The following periods are defined in this SAP for the purpose of analyses and reporting.

Pre-treatment period: It covers the time period which starts from the day of enrollment and lasts until the initiation of randomized double-blind treatment

Double-blind (DB) period: It starts at the time of the first dose of blinded treatment (BMS-986142 or placebo) and lasts until the date of the last dose of double-blinded treatment + 30 days or the start of first dose in long-term extension period.

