8.4 Baseline Measures

The baseline value is the last assessment taken prior to the first dose of study medication. In general, baseline value is the assessment taken on study Day 1 before the administration of study medication. If a measurement on Day 1 is missing, the last assessment taken at the screening period prior to the first dose of study medication will be used.

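### SAP 7.6 admits marked laboratory abnormalities to the double-blind period by calendar date, so the pre-dose Day 1 sample qualifies as on-treatment, in conflict with SAP 6.1 and the baseline rule

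*SAP*

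**What the plan says.** - **Inclusion rule.** SAP 7.6 says AEs and marked laboratory abnormalities are "included in the analysis of the DB period if the onset date is on or after first dose date" and fall no later than 30 days after the last dose. The lower bound is a date with no clock time.
- **Laboratory baseline.** The same section defines baseline as the "last non-missing result with a collection date-time less than the date-time of the first dose of study medication". SAP 8.4 adds that in general the "baseline value is the assessment taken on study Day 1 before the administration of study medication", with a screening value as fallback.
- **Period definition.** SAP 6.1 says of the double-blind period: "It starts at the time of the first dose of blinded treatment". Anything earlier belongs to the pre-treatment period.
- **Order of events on Day 1.** Protocol 4.5.1 states: "All drug dosing should occur after all study-related assessments, including blood draws, are completed". It adds that on Day 1 and at the later named visits "study drug will be administered in the morning at the study site and after blood samples have been collected". Protocol Table 5.1-2 schedules hematology, chemistry, lipids, immunoglobulins and urinalysis on Day 1.
- **Table affected.** SAP 7.6.7 presents, by test, the frequency of subjects with any marked abnormality in the double-blind period, for the As-treated population. It does not restate a lower bound.

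**The concern.** The Day 1 panel carries the date of first dose but precedes the dose. It therefore passes the date test in SAP 7.6 and also meets the date-time baseline rule a few lines later. One sample can then serve both as the reference value and as a result on treatment.

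What is at stake is how the laboratory safety table reads. SAP 7.6 names laboratory abnormalities among the main bases of the safety evaluation, and Protocol 1.5 gives raised transaminases as the only safety signal identified so far. With no testing planned, readers will compare raw frequencies across arms. An abnormality present before any drug would count as on-treatment in every arm, placebo included. That raises all rates and dilutes the active/placebo contrast.

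The SAP is more careful elsewhere: the ECG categories in 7.6.8.1 are restricted to recordings made after dosing. The laboratory rule has no such restriction.

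**Working it through.** The documents state no figure on this point, so there is none to reproduce.

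**Step 1: is the Day 1 sample eligible?** The onset date of a laboratory abnormality is taken here to be the collection date.

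| Rule | Test applied | Pre-dose Day 1 sample |
|---|---|---|
| SAP 7.6, inclusion | date on or after first-dose date | included |
| SAP 7.6, baseline | date-time before first-dose date-time | baseline |
| SAP 6.1, period | from the time of first dose | excluded |

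The first and third rules give opposite answers, and the SAP does not say which governs.

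**Step 2: share of admitted panels that are pre-dose.** This is for a completer, from Protocol Table 5.1-2.

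| Test | Scheduled panels | Date rule | Date-time rule | Pre-dose share |
|---|---|---|---|---|
| Hematology, chemistry | Day 1, Weeks 2, 4, 8, 12, follow-up | 6 | 5 | 1/6 = 17% |
| Lipids | Day 1, Weeks 8, 12, follow-up | 4 | 3 | 1/4 = 25% |
| Immunoglobulins | Day 1, Weeks 4, 12, follow-up | 4 | 3 | 1/4 = 25% |
| Urinalysis | Day 1, Week 12, follow-up | 3 | 2 | 1/3 = 33% |

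These are shares of eligible panels, not of subjects miscounted. Only values meeting the marked criteria enter the table.

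**Step 3: illustration of the effect.** No rates are in the documents, so all of these are assumptions. Let b be the proportion with a marked value on pre-dose Day 1 and t the true on-treatment incidence, independent of each other. The tabulated rate is

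1 − (1 − b)(1 − t).

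The tabulated risk difference is therefore (1 − b) times the true one. Take t = 3% on placebo and 9% on active: true ratio 3.0, true difference 6.0 points.

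| b | Placebo | Active | Ratio | Difference (points) |
|---|---|---|---|---|
| 1% | 1 − 0.99 × 0.97 = 3.97% | 1 − 0.99 × 0.91 = 9.91% | 2.50 | 5.9 |
| 2% | 1 − 0.98 × 0.97 = 4.94% | 1 − 0.98 × 0.91 = 10.82% | 2.19 | 5.9 |
| 5% | 1 − 0.95 × 0.97 = 7.85% | 1 − 0.95 × 0.91 = 13.55% | 1.73 | 5.7 |
| 10% | 1 − 0.90 × 0.97 = 12.70% | 1 − 0.90 × 0.91 = 18.10% | 1.43 | 5.4 |

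With 82 subjects per arm, the extra subjects counted for one test are 82 × b × (1 − t). On placebo that is 82 × 0.01 × 0.97 = 0.8 at b = 1% and 82 × 0.10 × 0.97 = 8.0 at b = 10%. If subjects abnormal on Day 1 tend to be abnormal later as well, fewer are added than independence implies.

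**The case against.** The strongest reply is that SAP 6.1 already settles the matter. SAP 7.6 speaks of the double-blind period, a defined term that begins at the time of first dose, and the baseline rule in the same section classes the Day 1 sample as pre-dose. On that reading nothing is miscounted. This stands far enough to rule out a claim that the Day 1 panel definitely is counted. It does not remove the problem: 7.6 is the specific rule for these summaries and states its own lower bound, so a programmer following it includes Day 1 and one following 6.1 does not. SAP 7.6 also invokes the sponsor's standard safety conventions, but it adds supplements defined in the SAP, and the date rule is one of these. The conventions are not in the documents, so they cannot be assumed to correct it.

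The objections about size largely stand:

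- The marked criteria are not given. If they are relative to baseline, a baseline value cannot qualify and the effect is nil.
- Protocol 3.3.2 excludes subjects with ALT, AST or total bilirubin at or above 1.5 × ULN, hemoglobin below 9 g/dL, neutrophils below 1,000/mm³ or platelets below 100,000/mm³. Screening lasts at most five weeks, so marked Day 1 values in these tests should be uncommon.
- The expected bias is equal across arms. The risk difference barely moves, and the SAP plans no ratio for laboratory data.
- Values by nominal visit and full listings would let a reader see which abnormalities date from Day 1.

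A reader might also take marked abnormalities to be a stated safety endpoint. SAP 4.3 lists clinically significant laboratory abnormalities; the marked-abnormality table is a descriptive summary.

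**Conclusion.** The point holds as an internal contradiction with a simple remedy. The rule as written in SAP 7.6 gives a wrong result for pre-dose Day 1 samples, while SAP 6.1 gives the right one.

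A reader might infer that every subject's baseline panel is counted as an on-treatment result. The documents do not support that: 6.1 points the other way, only values meeting unseen criteria would enter the table, and where the Day 1 value is missing the baseline is a screening sample dated before first dose. Nor do they support the inference that a liver signal would be hidden, given the transaminase limits at entry.

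If the date rule were applied, the ratio could be noticeably diluted (3.0 to between 2.5 and 1.4 under the assumed rates). The risk difference would lose at most 0.6 of 6.0 points. The real size cannot be determined: it is nil for criteria relative to baseline and probably small for tests limited at screening. SAP 7.6 plans no testing of these frequencies, and the co-primary endpoints, type I error and power are untouched. The wording should be corrected, but it does not threaten the trial's main conclusions.

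**What to change.** In SAP 7.6, separate the laboratory rule from the AE rule:

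- Count a laboratory result in the double-blind period only if its collection date-time is after the date-time of first dose, in line with 6.1 and the baseline definition. The upper limit of 30 days after the last dose stays.
- Treat a scheduled Day 1 sample with no recorded collection time as pre-dose.
- Never count the sample used as baseline as a double-blind result.
- Keep the date rule for AEs whose Day 1 onset time is missing, so that an event possibly arising after the dose is not lost.

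The cost is a few lines in the SAP and the matching line in the table specification. No new data are needed, because the baseline rule already uses collection and first-dose date-times.

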7.6.1 Adverse Events

The investigator will determine the intensity of each AE as mild, moderate, severe, or very severe. In addition, the investigator will determine the relationship of the AE to the administration of the study drug.

All AEs are coded and grouped into Preferred Terms (PT) by System Organ Class (SOC), using the latest approved version of the Medical Dictionary for Regulatory Activities (MedDRA) at the time of database lock. Listings and summaries will be based on the resulting SOCs and PTs.

AEs will be included in the frequency tabulations if they occur while a subject is on study medication up to and including 30 days after the last dose of study medication. These AE summaries will be based on proportions, which represent the number of subjects experiencing the AEs divided by the number of subjects received at least 1 dose of study medication in the current period.

All AE listings will indicate the unique subject identifier, age, gender, current treatment, the date of onset, the date of resolution, day of onset relative to the start of treatment, action taken, investigator’s assessment of severity and relationship to study drug. Additional listings will be provided for adverse events leading to discontinuation and adverse events without recorded resolution. Summaries of adverse events will include adverse events, adverse events by intensity (based on CTC grade) and adverse events by relationship.

Where a subject has the same adverse event, based on preferred terminology, reported multiple times in a single analysis period, the subject will only be counted once at the preferred terminology level in adverse event frequency tables.

Where a subject has multiple adverse events within the same system organ class in a single analysis period, the subject will only be counted once at the system organ class level in adverse event frequency tables.

When a subject has the same adverse event, based on preferred terminology, reported multiple times in a single analysis period, the following criteria, in order of precedence, will be used to select the event to be included in summary tables:

- Relationship to study medication
- Intensity of event
- Onset date and time

When reporting adverse events by intensity, in addition to providing a summary table based on the event selection criteria detailed above, summary tables will also be provided based on the most intense event during the analysis period - independent of relationship to study medication. For these tables, the following criteria, in order of precedence, will be used to select the event to be included in summary tables:

- Intensity of event
- Onset date and time

Subjects will only be counted once in the 'Total' at their maximum intensity, regardless of SOC or PT.

Any reported AEs that occur more than 30 days after the last dose of study drug will be excluded from safety summaries. Any reported AEs that occur more than 30 days post the last dose of study drug will appear in the listing.

Summary information (the number and percent of subjects by treatment) will be tabulated for the following AEs:

- All AEs including clinical and laboratory AEs
- Most common AEs (reported in 5% of subjects or more in any treatment group)
- All related events
- Serious AEs (SAEs)
- Discontinuations due to AEs

Laboratory AEs are laboratory changes identified by the investigator as AEs and thus reported on the AE pages of the eCRF. The intensity of all related AE will be provided if enough data warrants the analysis.

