- Subgroup analysis of above endpoints by region where applicable (e.g., if any region consists of more than 50% of total subjects and region is classified by North America, Latin America, Europe and Rest of World. One or more regions may be combined for analysis if only limited data in individual region is available).

Descriptive safety analysis:

For the following pre-specified safety endpoints:

- AE/SAE (including but not limited to hypertension, diarrhea, neutropenia)
- Change from baseline in vitals including systolic blood pressure (SBP) and diastolic blood pressure (DBP).

The study will be stopped if intolerable safety events are identified in all treatment arms. If intolerable safety events are identified in 1 or 2 treatment arms, these arms will be dropped and

the study will be continued with caution. New dose levels may be added based on the exposure response analysis (not greater than 350 mg daily). If intolerable safety events show a clear relationship with higher exposure of BMS-986142, a lower dose will be selected where the predicted exposure in ~ 90% of subjects does not exceed the exposure ranges associated with safety findings.

Based on the totality of safety and efficacy considerations, ineffective doses will be stopped at Week 12 and unsafe dose will be stopped immediately.

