2 STUDY DESCRIPTION

2.1 Study Design

This is a 12 week randomized, double-blind, placebo-controlled, dose-ranging study with adaptive design features based on an interim analysis. The study will initially have a Screening Period (with 2 screening visits for subjects that require DMARD washout) and be followed by up to 12 weeks of DB treatment and a 30 day follow-up period.

Four treatments will be administered: placebo, 100, 200, and 350 mg of BMS-986142 daily for 12 weeks. Based on the Week 4 interim analysis, one or more BMS-986142 doses and/or sample size may be subsequently modified.

Screening Period:

[figure not shown]
The standard duration of the Screening Period is up to 30 days, with two Screening Visits allowed for subjects who require washout of hydroxychloroquine/chloroquine and/or sulfasalazine. Subjects who are on hydroxychloroquine/chloroquine and/or sulfasalazine in combination with MTX will have hydroxychloroquine/chloroquine and/or sulfasalazine discontinued at the beginning of the Screening Period as they need to be off those medications for at least 30 days and need to be rescreened prior to randomization (Day 1). Should more time be needed, the duration of the Screening Period may be extended up to another week (total of five weeks) depending on current DMARDs washout, drug stabilization, MRI technical issues, and subject scheduling.

Subjects with moderate to severely active RA who have had an inadequate response to MTX or up to 2 TNF inhibitors will receive BMS-986142 or placebo daily for up to 12 weeks, followed by a 30 day follow-up period.

Double-Blind Period:

Upon meeting the inclusion criteria and none of the exclusion criteria and completing the screening period, approximately 328 subjects will be randomized to 1 of the 4 treatment arms in an equal ratio as shown in the study schematic below.

Figure 1: Study Design Schematic

During this period, the dose of methotrexate, NSAIDs, and oral prednisone (or its equivalent) should remain stable. Intra-articular corticosteroid injections and intra-muscular injections are not permitted. Analgesics are permitted with certain restrictions (see [Section 3.2](#)).

At the end of the DB period, alternate therapies for RA should be discussed with subjects.

Interim Analyses:

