7.4 Extent of Exposure

7.4.1 Study Therapy

In general, extent of exposure will be summarized for the As-treated analysis population in two ways:

- by the number of study drug doses. Frequency distribution of number of doses will be summarized
- by the number of days the subject is known to be on study drug, ignoring any dosing interruptions

In general, exposure to study drug during the double-blind (DB) period in days is calculated as:

For subjects who discontinue study medication,

- Exposure = (date of last DB dose - date of first DB dose + 1) + 30.

The offset of 30 days represents 30 days of follow-up after last dose and is a lot longer than 5 times of half-life of the study medication. The frequency will be presented according to the duration ranges (in days) : <28, 29-56, 57-84 and so on.

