If the predictive probability of $\Delta\Delta\text{DAS28}$ improvement being greater than 0.6 is lower than 20% in all active treatment arms, BMS team may recommend stopping further enrollment and continuing those subjects receiving therapy up to 12 weeks.

Descriptive efficacy analysis (other efficacy endpoints):

In addition to Bayesian predictive analysis above, the following as-observed clinical data up to database lock will be summarized at the time of Week 4 interim analysis to facilitate decision-making.

- ACR20/50/70 response over time
- DAS28-CRP < 2.6 , DAS28-ESR < 2.6 , CDAI ≤ 2.8 , SDAI ≤ 3.3 and Boolean remission over time
- Change from baseline in DAS28-CRP, DAS28-ESR, CDAI, SDAI over time.

Descriptive safety analysis:

For the following pre-specified safety endpoints:

- AE/SAE (including but not limited to hypertension, diarrhea, neutropenia)
- Change from baseline in vitals including systolic blood pressure (SBP) and diastolic blood pressure (DBP).

The study will be stopped if intolerable safety events are identified in all treatment arms. If intolerable safety events are identified in 1 or 2 treatment arms, these arms will be dropped and

the study will be continued with caution. New dose levels may be added based on the exposure response analysis (not greater than 350 mg daily). If intolerable safety events show a clear relationship with higher exposure of BMS-986142, a lower dose will be selected where the predicted exposure in ~ 90% of subjects does not exceed the exposure ranges associated with safety findings.

Based on the totality of safety and efficacy considerations, unsafe dose arm will be stopped immediately. The dose arm(s) that are projected to be ineffective will continue till the end of double-blind period for subjects already taking at least one dose of study medication and no new subjects will be enrolled into ineffective dose arm(s).

[REDACTED]

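### If an arm is stopped early for safety, the SAP's crude adverse-event proportions will understate that arm's event burden relative to placebo and the other arms

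*SAP*

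**What the plan says.** SAP 7.6.1 defines the summary measure, with everyone dosed in the period as the denominator: "These AE summaries will be based on proportions, which represent the number of subjects experiencing the AEs divided by the number of subjects received". Events count while the subject is on drug and "up to and including 30 days after the last dose of study medication". For anything later, the rule is: "Any reported AEs that occur more than 30 days after the last dose of study drug will be excluded from safety summaries"; such events are listed only. All AEs, common AEs, related AEs, SAEs and discontinuations due to AEs are tabulated as number and percent. SAP 7.6.2 has the events of special interest summarised by treatment group, with no other measure named.

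Planned treatment is the same length in every arm: "placebo, 100, 200, and 350 mg of BMS-986142 daily for 12 weeks" (SAP 2.1). The follow-up visit falls at about Day 114 (Protocol Table 5.1-2).

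The stopping rules are asymmetric. SAP 7.9: "Based on the totality of safety and efficacy considerations, unsafe dose arm will be stopped immediately". Protocol 8.5: "ineffective doses will be stopped at Week 12 and unsafe dose will be stopped immediately". SAP 7.9 adds that treated subjects in an arm projected to be ineffective carry on to the end of the double-blind period. Protocol section 7 also lets the DMC recommend terminating a treatment group at its regular reviews.

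Exposure is summarised separately (SAP 7.4.1), partly "by the number of days the subject is known to be on study drug, ignoring any dosing interruptions", with a formula that adds 30 days after last dose. It is not used as a denominator for adverse events. The readable SAP contains no incidence rate and no time-to-event summary of adverse events. SAP 7.6 also relies on the sponsor's standard safety conventions, which are not reproduced.

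**The concern.** A proportion of treated subjects is comparable between arms when the arms are observed for similar lengths of time. The plan's own safety rule breaks that condition, and only for the arm thought to be harmful. Subjects in that arm stop at whatever week they have reached, and their counting window closes 30 days later. Protocol 3.6 asks for continued follow-up after study drug stops, but later events do not enter the summaries, so this does not repair the imbalance.

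At stake is the description of dose-related safety in the final report. The SAP specifies no testing of adverse events, so readers will judge dose-response from these percentages. The event that triggered the stop will probably still stand out. Other events in the same arm, such as infections, hypertension or neutropenia, were not necessarily in excess at the stop. They would be understated without anything in the table to show it.

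**Working it through.** The plan states no figure for this effect. The one number that can be checked is the planned window: 12 weeks × 7 = 84 days, and 84 + 30 = 114 days, which agrees with the Day 114 visit.

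**Inputs from the documents.** Full window 114 days. The interim takes place when about 20 subjects per arm have reached Week 4 (SAP 7.9). Up to about 82 subjects per arm.

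**Assumed inputs (not in the documents).** Constant hazard, the same on drug and in the 30-day tail; accrual a = 1, 2 or 4 subjects per arm per week, continuing to the stop; lag L = 2, 4 or 8 weeks from the interim data point to the stop; full-length risk p = 20% or 40%; true hazard ratio (HR) of 1, 1.5 or 2.

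**Formulas.**
- Stop time in weeks from first entry: T = 20/a + 4 + L.
- Window for a subject entering at week t: w = min(84, 7(T − t)) + 30 days.
- Daily hazard: h = −ln(1 − p)/114.
- Crude proportion in the stopped arm: mean over subjects of 1 − exp(−HR × h × w).

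**One scenario in full: a = 2, L = 4.** T = 10 + 4 + 4 = 18 weeks, with 36 subjects entering at weeks 0, 0.5, …, 17.5. The 13 who enter by week 6 complete 12 weeks. The other 23 have 0.5 to 11.5 weeks, summing to 0.5 × (23 × 24/2) = 138. Mean time on drug = (13 × 12 + 138)/36 = 8.17 weeks, or 57.2 days, so the mean window is 87.2 days against 114. With p = 0.40, h = 0.5108/114 = 0.00448 per day. The crude proportion is 31.8% at HR 1, against 40% at full length.

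**All scenarios, p = 40%.** Full-length values are 40% (HR 1), 1 − 0.6^1.5 = 53.5% (HR 1.5) and 1 − 0.6² = 64% (HR 2).

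| Accrual/arm/week | Lag (weeks) | T (weeks) | Mean window (days) | HR 1 | HR 1.5 | HR 2 |
|---|---|---|---|---|---|---|
| 1 | 2 | 26 | 96.2 | 34.6% | 46.8% | 56.6% |
| 1 | 4 | 28 | 97.5 | 35.0% | 47.3% | 57.1% |
| 1 | 8 | 32 | 99.6 | 35.6% | 48.1% | 58.0% |
| 2 | 2 | 16 | 83.8 | 30.8% | 42.1% | 51.4% |
| 2 | 4 | 18 | 87.2 | 31.8% | 43.4% | 52.8% |
| 2 | 8 | 22 | 92.0 | 33.3% | 45.2% | 54.8% |
| 4 | 2 | 11 | 69.4 | 26.4% | 36.6% | 45.2% |
| 4 | 4 | 13 | 76.0 | 28.4% | 39.1% | 48.0% |
| 4 | 8 | 17 | 85.0 | 31.1% | 42.5% | 51.8% |

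At equal hazard the relative understatement runs from 1 − 35.6/40 = 11% to 1 − 26.4/40 = 34%. A 20% event shows as 12.6-17.6%.

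**Direction against placebo.** If every subject stopped on the same treatment day D, the two crude proportions would be equal at HR = 114/(D + 30): 2.59 for day 14, 1.97 for day 28, 1.58 for day 42 and 1.33 for day 56. With staggered entry (accrual 0.5 to 5 per arm per week, lag 0 to 4 weeks) the break-even HR is about 1.1 to 2.0. Above it, the stopped arm still shows more events than placebo. In the table, HR 1.5 falls below 40% only at 4 per week with a lag of 2 or 4 weeks, and HR 2 never does.

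**The case against.** A reader might infer that the stopped arm must look safer than placebo. The documents do not support that. Shorter observation lowers the proportion but does not fix its direction. An arm is stopped for intolerable safety events, so it is selected for an excess, and at HR 2 that excess stays visible in every scenario above.

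A reader might also infer that the choice of dose is compromised. The plan does not support that either. The unsafe dose has already been dropped at the interim, when equal randomisation gives the arms similar follow-up, and any new dose is guided by exposure-response analysis rather than by the final tables.

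Further points stand. The problem arises only if some, but not all, arms are stopped for safety. Nothing in the documents shows that this happened, and the Protocol synopsis says the end of recruitment was unrelated to adverse events. Adverse events are described, not tested. Exposure tables and onset days in the listings let a careful reader see unequal follow-up. If events cluster early, the shortfall tends to zero, and a person-time rate would then overstate the stopped arm. The unseen sponsor conventions might already include a rate.

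These points limit the concern but do not remove it. Being able to notice the imbalance is not the same as correcting it. Selection for an excess protects only the events that caused the stop. The SAP text itself commits to no measure that allows for follow-up time.

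**Conclusion.** The concern holds as a conditional point. If an arm is stopped for safety, at the interim or on DMC advice, the tables in SAP 7.6.1-7.6.2 will understate its adverse-event burden relative to placebo and the other arms. Under the stated assumptions, a 40% event at equal hazard shows as 26-36%, and a true HR of 1.5 shows as about 37-48% instead of 53.5%. Whether the arm falls below placebo depends on the true HR and the speed of accrual.

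These sizes rest on a constant hazard and on accrual, lag and event rates that the documents do not give. Arms dropped for inefficacy are not affected, because their treated subjects complete the double-blind period. This is an inexpensive improvement to a pre-specified adaptive plan, not a flaw that undermines the trial's safety conclusions.

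**What to change.** In SAP 7.6.1-7.6.2, state that if any arm is stopped early for safety, the tables of AEs, SAEs, discontinuations due to AEs and events of special interest will also show, beside the crude proportions, one or both of:

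- first-event incidence per 100 patient-years, with time from first dose to the earlier of first event or last dose + 30 days;
- Kaplan-Meier cumulative incidence at a common day that the stopped arm's follow-up reaches. Day 114 may be too late: with T = 11 weeks the longest window is 77 + 30 = 107 days.

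State also that between-arm descriptions will take the unequal follow-up into account.

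The cost is SAP wording and an extra column. First-dose, last-dose and onset dates are already used in SAP 7.4.1 and 7.6.1, and the exposure formula already adds the 30 days. The downside is that rates assume a roughly constant hazard, which the common-day cumulative incidence does not, so the crude proportions should stay.
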